### 6.3 Subgroup analyses

We will examine the following subgroups:

- baseline oxygenation status (moderate PaO2/FiO2 <20 but >13kPa, and severe <13kPa)

- Illness severity on admission
- previous site experience with APRV (APRV naïve vs previous APRV experience)

These subgroup analyses will be performed using intention to treat. We will use the primary outcome as the dependent variable and interaction with treatment and sub-group. We will use linear regression models to assess the subgroup effect, using interaction terms. As these analyses are posthoc analyses not powered for any effect size, emphasis will not be based on the statistical testing, rather the point estimates and 95% Cls.

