### 2.8 Randomisation

### 2.8.1 Randomisation

Randomisation will occur once eligibility has been confirmed and consent obtained. Participants will be randomised via randomly permuted blocks using an automated web-based system on a one-toone basis, stratified by site and prior enrolment into the Awake Prone Positioning and Protect Airways trials, using a computer-generated randomisation schedule managed by the Warwick CTU. We have selected a parallel group RCT design to minimise selection bias and ensure against accidental bias.

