### 6. STATISTICAL ANALYSIS

### 6.1 **Power and sample size**

The RELEASE trial will recruit a total of 710 (355 per arm) participants (using 90% power and 5% significance level).

The parameter estimates for this trial have been derived as follows:

(a) Effect size of 2-days reduction: Given our (Figure 1) and previous meta-analyses[8-11] showed a reduction of IMV duration with APRV of 3.3-5.4 days, an effect size of 2 days is conservative and can be realistically achieved.

[figure not shown]
(b) Median duration of ventilation on the control arm: the duration of ventilation varies in the UK from 7 to 14 days in reported studies (i.e., 7 days- BREATHE trial [23]; 14.1 days -OSCAR trial[24]. National reporting from the Intensive Care National Audit & Research Centre (ICNARC) Case Mix Programme Database 2019 indicates a duration of 6 days. Taking our trial population and comparing this to that reported in previous studies, we anticipate that the duration of ventilation in the control arm would be approximately 9 days.

(c) Loss to follow-up: In the previous CCU studies, loss to follow-up ranges from 0% to 3% (1.1% -BREATHE trial [23]; 0% - OSCAR trial[24] 0.4% - HARP-2 trial[25]; 0.5% - HARP trial; 3% - REST trial[26]). We have assumed a worst-case scenario here and used 5% as our loss to follow-up rate.

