### 6.2.3.2 Primary outcome analysis

Primary outcome and the Estimand Framework

In addition to the objectives, interventions and the population already stated above, the following define the Estimand framework that will be used for the RELEASE trial, in line with the ICH E9 (R1) addendum on Estimand and sensitivity analyses in clinical trials.[23]

Variable (outcome): Our main variable (outcome) of interest is ventilation duration, from the time of randomisation to successful extubation or death. 'Successful extubation' will be defined using the core outcome set[21] definition i.e., the time point a patient is free of ventilatory (invasive or non-invasive) support for >48 hours.

Summary measure and the primary Estimand: Ventilation duration will be determined as the time of successful extubation/death minus the time from the point of randomisation (in hours/mins). The statistical analysis for this outcome will be performed using the treatment policy strategy (i.e., intention-to -treat). Statistical summaries of ventilation duration will be made using median and interquartile range (IQR). We will use a Cox proportional hazard regression model to estimate the treatment difference reporting hazards ratios and their 95% confidence intervals (CIs), using both unadjusted and adjusted estimates. We will report the mean difference with 95% CIs using linear regression.

Intercurrent events (ICEs) and strategies for handling ICEs: post-randomisation events that may affect the interpretation of the primary outcome include: (a) crossover; (ii) non-adherence (including discontinuation of treatment); and (iii) death. Rates of crossover and non-adherence will be added using the principal stratum strategy. We will use the inverse probability weighted analysis method[24] to assess the treatment effect, having taken account of these events. The composite strategy will be used to assess the effect of death, with ventilation duration. We will use the Pocock's win-ratio method[25] and also assess the interaction of ventilation duration with mortality status, bearing in mind the interaction term may not be powered to detect differences.

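### Subgroup effects on the primary outcome are estimated only in days by linear regression, not on the hazard-ratio scale of the primary analysis, and are mislabelled post hoc

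*Protocol*

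**What the plan says.** Section 6.3 lists three subgroups: baseline oxygenation, illness severity on admission, and the site's previous experience with APRV. It takes the primary outcome as the dependent variable and states "We will use linear regression models to assess the subgroup effect, using interaction terms". It mentions neither a Cox interaction nor a transformation of duration. It then describes the status of the analyses: "As these analyses are posthoc analyses not powered for any effect size". Emphasis is to lie on point estimates and confidence intervals rather than on tests.

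Section 6.2.3.2 treats the outcome as a time from randomisation to successful extubation or death. It estimates the treatment difference by Cox regression, unadjusted and adjusted, and adds a second summary: "We will report the mean difference with 95% CIs using linear regression".

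The oxygenation subgroup in section 6.3 sets moderate as below 20 but above 13 kPa, and severe as below 13 kPa.

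**The concern.** The main effect is a hazard ratio, while every subgroup effect is a difference in days. A reader who asks whether the hazard ratio is consistent across subgroups gets no answer from the planned analysis. An incomplete duration must also be dropped, filled in or taken at face value in ordinary linear regression, whereas the Cox model can use it as censored.

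The two scales need not agree. Where patients are ventilated for longer, the same hazard ratio corresponds to more days saved. Two of the three subgroups are severity-based, so different control-arm durations are plausible. A difference in days could then be read as evidence that APRV works better in one group when its relative effect is the same in both. Playing down the tests does not protect against this, because the point estimate itself shifts.

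**Working it through.** **Inputs from the protocol.** Section 6.1 gives "The RELEASE trial will recruit a total of 710 (355 per arm) participants (using 90% power and 5% significance level"; "a) Effect size of 2-days reduction"; "we anticipate that the duration of ventilation in the control arm would be approximately 9 days" (the item is headed as a median); and "used 5% as our loss to follow-up rate". Section 2.8.1 gives 1:1 allocation.

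**Assumptions, not in the protocol.** A two-sided test, exponential durations, subgroup control medians (mostly within the 7 to 14 days that section 6.1 reports across UK studies), the share of patients in each subgroup, and a 60-day cap on duration.

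**Step 1: the plan's own figure.** Exponential medians of 9 and 7 days give HR = 9/7 = 1.286.
- Freedman: (1.960 + 1.282)² × [(1 + HR)/(HR − 1)]² = 10.51 × 8² = 673 events. Dividing by 0.95 gives 709, or 355 per arm and 710 in total.
- Schoenfeld: 4 × 10.51/(ln 1.286)² = 666 events. Dividing by 0.95 gives 702.

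The stated size fits a hazard-ratio design. A two-means formula also reaches 710, but only with an SD of 8 days, which the protocol does not state.

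**Step 2: constant hazard ratio, uncapped.** Exponential mean = median/ln 2, so the mean saving = (median/ln 2) × (1 − 7/9).
- Control median 7: 10.10 × 2/9 = 2.24 days.
- Control median 12: 17.31 × 2/9 = 3.85 days. The gap from 7 is 1.60 days (unrounded).
- Control medians 8 and 11: 2.56 and 3.53 days, gap 0.96 (unrounded).
- Equal control medians: gap 0.

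**Step 3: the same with a 60-day cap.** Mean up to day 60 = (median/ln 2) × (1 − 2^(−60/median)). APRV medians are 7 × 7/9 = 5.44 and 12 × 7/9 = 9.33.
- Shorter group: 10.07 − 7.85 = 2.22 days.
- Longer group: 16.77 − 13.31 = 3.46 days.
- Gap: 1.24 days.

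**Step 4: simulation.** N = 710, HR 9/7 in both subgroups, 60-day cap, 3,000 trials per row. A negative interaction means a larger saving in the longer-duration subgroup. The last column is an exponential log-rate interaction, standing in for Cox.

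| Control medians | Share in longer group | Mean interaction (days) | Sampling SD | Linear test rejects | HR-scale test rejects |
|---|---|---|---|---|---|
| 9/9 | 50% | 0.0 | 1.70 | 5.5% | 5.7% |
| 8/10 | 50% | −0.5 | 1.66 | 5.9% | 4.5% |
| 7/12 | 50% | −1.2 | 1.76 | 10.5% | 4.9% |
| 7/12 | 30% | −1.25 | 2.09 | 16.0% | 5.4% |
| 7/14 | 50% | −1.6 | 1.89 | 11.9% | 4.8% |
| 6/14 | 30% | −1.9 | 2.26 | 25.3% | 5.5% |

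With Weibull durations (shape 1.3), medians 7/12 and an equal split, the mean interaction is −1.0 days and the linear test rejects 11.6%.

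With HR = 1 and medians 7/14 the mean interaction is about 0, but the linear test still rejects 10.6% with 30% in the longer group (5.4% with an equal split). Part of the excess in uneven splits therefore comes from unequal variances and not from the shift in days.

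**Step 5: points that need no arithmetic.** The subgroups, their model, dependent variable and analysis population are all stated in the protocol, so they are pre-specified. With moderate strictly above 13 kPa and severe strictly below, a value of exactly 13 belongs to neither.

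**The case against.** Section 6.2.3.2 itself lists a linear-regression mean difference, and section 6.1 sets the target effect in days, so the subgroup model matches one of the two stated effect measures. Days saved is a legitimate additive quantity and bears on cost. Interaction also depends on scale in both directions: a constant 2-day saving in medians gives a hazard ratio of 7/5 = 1.40 in one group and 12/10 = 1.20 in the other. All of this stands. It supports keeping days as a supplement, but not as the only subgroup scale.

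A reader might infer that false effect modification by severity *will* appear. The document does not support that. It needs both a real treatment effect and different control durations, and no durations by subgroup are given. Death ends the duration, and section 1.1 cites mortality of about 40%, so sicker patients need not have longer durations. The sampling SD is about as large as the shift or larger in nearly all scenarios.

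A reader might also blame linear regression for counting an early death as a short duration. The Cox model of the same outcome ends at death too, so this does not separate the methods.

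Nor does the protocol say that the outcome is cut off at day 60. Section 2.9.4.2 ends the intervention then, while section 3.1 collects the primary outcome up to CCU discharge. Incomplete durations should be few: section 2.3 expects completeness above 95%, and 5% of 710 is about 36 participants.

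Finally, the analyses are acknowledged to be unpowered, and a later SAP may add detail. Section 6.3 nevertheless fixes the model and the label itself.

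**Conclusion.** Three points hold without any assumption. The subgroup analysis is not on the scale of the primary hazard ratio and cannot handle censoring. The post hoc label is wrong. A value of exactly 13 kPa has no group.

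The distortion in days is conditional. With HR 9/7 and assumed control medians of 7 and 12 days it is about 1.6 days uncapped or 1.2 days with an assumed 60-day cap, against a 2-day design effect that section 6.1 relates to a median. The false-interaction rate is then about 10-16% instead of 5%. With medians of 8 and 10 and an equal split it is close to nominal, and with equal medians there is no shift. Neither size nor direction can be fixed from the document. The matter concerns exploratory analyses, so the sample size and the primary conclusion do not depend on it.

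**What to change.** In section 6.3:

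- Make the treatment-by-subgroup interaction in the primary Cox model the main subgroup analysis, reported as a ratio of hazard ratios with 95% CI.
- Keep the difference in days as a supplementary additive-scale summary, either with robust standard errors or as a restricted mean difference over a stated horizon.
- Replace the post hoc label with pre-specified, exploratory and not powered.
- Assign a PaO2/FiO2 of exactly 13 kPa to one of the two analysis groups.

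The cost is a change of wording before analysis and one extra model per subgroup. No additional data or participants are needed.

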### 6.4 Interim analysis

We will not carry out a formal interim analysis.

### 6.5 Health Economic Evaluation

We will conduct a prospectively planned within-trial cost-utility analysis with a six-month time horizon from an NHS hospital care perspective (primary economic analysis).

Costs will be analysed for the period from randomisation to 6 months post randomisation. Initial hospitalisation resources (randomisation to initial discharge) will be identified from clinical records using case report forms (CRFs) and potentially enriched using data obtained through linkage to routine datasets (e.g., Hospital Episode Statistics (HES), Intensive Care National Audit & Research Centre (ICNARC)). The data of interest here include information on critical care (e.g. CCU length of stay and organs supported), inpatient care (e.g. length of stay -where applicable including transfer to another unit for ongoing treatment- and reason for admission), and emergency care.

Post-discharge hospital resource use at 2- and 6-months post randomisation will be identified from data obtained from participant completed resource use questionnaires (RUQs) and if available enriched using data obtained through CRFs/linkage. These data will comprise of information on critical care, inpatient care, outpatient care, and emergency care.

Our approach with regard to resource utilisation is to focus on the relevant resource items for patients who are receiving IMV, recognising that their underlying reasons for admission and other care needs are complex and heterogeneous. This means we have selected a hospital care perspective as our primary analysis. Our experience in this field suggests that primary, other community and social care are not likely to be as relevant to the intervention given that economic evaluation is an incremental analysis. Additionally, our PPI consultation has repeatedly stressed the need to avoid the burden of questionnaire completion during recovery. However, to align with other studies in the CORRECT confederation, we propose to use a brief resource use questionnaire to allow us to collect post-discharge NHS Community and Social care resource use. These data will allow us to conduct a secondary analysis from an NHS and personal social services perspective.

Data on resource items usage will be converted into costs using up-to-date sources of NHS and PSS reference costs [ref].

Generic health-related quality of life will be assessed at 2- and 6-months using the EQ-5D-5L questionnaire. EQ-5D-5L scores will be converted to health status scores using the UK value set recommended by NICE guidance at the time of analysis.[26] We will calculate patient-level Quality adjusted life year (QALY) estimates using the trapezoidal rule using utilities generated via the EQ-5D-5L in surviving patients, with baseline utility (which cannot be self-reported be critically ill patients) estimated following a method used in other CCU studies conducted by our group.[27, 28]

Selected statistical methods will deal with skew, baseline imbalance, and sampling uncertainty as appropriate. Every effort will be made to minimise missingness. If missingness of patient-level costs or QALYs is  $\leq$  5%, the primary analysis will use complete case data.[29] If missingness exceeds 5%, mechanisms of missingness will be explored and multiple imputation methods will be applied to impute missing data.

We will use bootstrapped bivariate analyses of costs and QALYs to generate within trial incremental cost per QALY estimates and confidence intervals. Findings will be analysed and visualised as cost-effectiveness acceptability curves [30] and net monetary benefit approach which will show the probability that APRV is the optimal choice over a range of possible values of the ceiling ratio.

If findings are non-convergent at six months, we will explore the sensitivity of cost-effectiveness to extrapolation of costs and benefits beyond the trial time horizon, via a suitable decision model or parametric survival analysis model in a secondary analysis.

Details of the prospective plan and analysis will be described in the Health Economics Analysis Plan (HEAP) written by the trial health economists in line with guidance from Warwick CTU SOP 21. Reporting will follow the Consolidated Health Economic Evaluation Reporting Standards (CHEERS) statement.[31]

## 7. TRIAL ORGANISATION AND OVERSIGHT

### 7.1 Sponsor and governance arrangements

The University of Warwick will act as trial sponsor. Full details are listed in section 9.1 of the CoReCCT Master Protocol.

### 7.2 Ethical approval

Full details are listed in section 9 of the CoReCCT Master Protocol.

### 7.3 Trial Registration

We will prospectively register the trial with an appropriate trial registry.

### 7.4 Notification of serious breaches to GCP and/or trial protocol

Full details are listed in section 9.5 of the CoReCCT Master Protocol.

### 7.5 Indemnity

Full details are listed in section 9.6 of the CoReCCT Master Protocol.

### 7.6 Trial timetable and milestones

The total planned project duration is 52 months. A summary of key trial milestones is shown below.

### **Table 6: Project Milestones**

	Month	Recruitment
Set-up	1-7	N/A
Internal Pilot	8-15	78
Recruitment	16-39	710
Follow up	40-45	N/A
Analysis, reporting & dissemination	46-52	N/A

### 7.7 Administration

The trial co-ordination will be based at WCTU, University of Warwick. Full details are listed in section 9.7 of the CoReCCT Master Protocol.

### 7.8 Trial Management Group (TMG)

Full details are listed in section 9.9 of the CoReCCT Master Protocol.

### 7.9 Trial Steering Committee (TSC)

Full details are listed in section 9.11 of the CoReCCT Master Protocol.

### 7.10 Data Monitoring Committee (DMC)

Full details are listed in section 9.10 of the CoReCCT Master Protocol.

### 7.11 Essential Documentation

Full details are listed in section 9.14 of the CoReCCT Master Protocol.

### 7.12 Financial Support

The trial has been funded by a grant from the National Institute of Health and Care Research Health Technology Assessment programme (NIHR154501). Full details are listed in section 9.13 of the CoReCCT Master Protocol.

### 7.13 Safeguarding Researchers and Research Participants

Full details are listed in section 9.15 of the CoReCCT Master Protocol.

### 8. MONITORING, AUDIT AND INSPECTION

A Trial Monitoring Plan will be developed by the trial team and a member of the WCTU Quality Assurance team and approved by the domain chief investigator. A risk-based proportionate approach will be outlined in the monitoring plan to facilitate remote and off-site monitoring, except where onsite monitoring is deemed to be required. Further details on monitoring, audit an inspection is detailed in the CoReCCT master protocol.

### 8.1 Training

Principal investigators, research team members involved in approaching patients/ consultees for consent, and members of the WCTU team will be required to undergo GCP training. PIs will be required to provide a copy of their GCP certificate and a signed and dated CV to WCTU. Site staff listed on the delegation log should ensure their CVs and, where appropriate, evidence of GCP training is available to WCTU on request.

Training materials on trial procedures, including eligibility assessment and consent processes, will be developed by WCTU to standardise trial processes for site research staff. The training will take a modular approach, such that individuals will only need to undertake training relevant to their training role. Training may be delivered face-to-face (in-person or via video call) or through completion of the web-based training package. In-person training is required to be delivered by a member of WCTU staff or a member of the site team approved by the PI. Completion of training for individuals listed on the delegation log will be recorded in the site file.

WCTU staff that are new to the trial will follow a thorough induction plan developed by the Trial Manager.

### 8.2 Data Quality

Full details are listed in section 10.4 of the CoReCCT Master Protocol.

### 8.3 Visits to Sites

Full details are listed in section 10.1 of the CoReCCT Master Protocol.

## 9. PATIENT AND PUBLIC INVOLVEMENT (PPI)

Our two PPI co-applicants will advise on all trial aspects and will participate in TMG and PPI advisory group meetings.

We will continue to embed meaningful patient and public involvement throughout the project. We will convene a PPI group of approximately 6-members with a membership that reflects the diversity of people at risk of acute hypoxaemic respiratory failure. The PPI group will meet regularly throughout the trial to provide advice and support to the trial management group. PPI advisory group meetings will seek input on: final trial protocol, participant facing documents, ongoing trial awareness and dissemination activities.

We will identify at least two PPI members to become independent members of the Trial Steering Committee. This group will be responsible for the oversight of the trial and advising the Sponsor and Funder in accordance with the NIHR terms of reference for steering committees.

### 10. DISSEMINATION AND PUBLICATION

The trial investigators named in this document will have access to data and be involved in drafting of manuscripts, abstracts, press releases and any other publications arising from the trial. Authorship will be determined in accordance with the ICMJE guidelines and other contributors will be acknowledged.

Results will be reported as papers in peer reviewed journals and presentations at academic conferences. A lay results summary will be available via the trial website. Executive summaries will be sent to relevant professional societies and charities.

